#### 8.1.3 TREATMENT VISIT (VISIT 3) (DAY 0)

Enrolled subjects will receive bilateral cryoablation treatment in-office. The Treatment Visit (Visit 3) may occur on the same calendar day as Visits 1 and 2 and must be completed within thirty (30) days from Visit 1 and no later than seven (7) calendar days of Visit 2.

Subjects will begin being assessed for Adverse Events (AEs) starting at Visit 3, with any AEs occurring at Visit 3 or after through study completion (see Section 8.4).

At Visit 3, the following study activities will be completed:

1. Concomitant Medication usage will be updated.
2. Physician will perform bilateral cryoablation treatment with the ClariFix device, per IFU. See Section 6.
  - a. Subject will be asked for a Verbal Pain Numeric Rating Scale (NRS) immediately after cryoablation treatment at each individual treatment location (see Section 8.3.2) and documented.
3. Subject will be monitored and assessed for Adverse Events.
  - a. Should post-procedure discomfort or pain be experienced, in addition to an adverse event form, subject will be asked for a Verbal Pain NRS.
4. Subject will be scheduled for 1-Week Follow-up (Visit 4).

---

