1.2 SCHEMA

1.3 SCHEDULE OF ACTIVITIES (SOA)

Study Activity	Screening (V1) Day -30 to 0	Baseline (V2) Day -7 to 0	Treatment (V3) Day 0	1-Week Follow-up (V4) Day 7 (±3 days)	1-Month Follow-up (V5) Day 30 (±7 days)	3-Month Follow-up (V6) Day 90 (±14 days)	Unscheduled b
Informed Consent	X						
Demographics Questionnaire	X						
Medical History	X						
Concomitant Medication	X	X				X	X
Physical/Endoscopic Nasal Exam	X			X c	X	X	X
Reflective Total Nasal Symptom Score (rTNSS)	X	X			X	X	X
Inclusion/Exclusion Criteria	X	X					
Nasal Obstruction Symptom Evaluation (NOSE) Instrument		X			X	X	
Sino-Nasal Outcome Test (SNOT-22)		X			X	X	
Visual Analog Scales – Nasal Symptoms		X			X	X	
Mini Rhinoconjunctivitis Quality of Life Questionnaire (MiniRQLQ)		X			X	X	
Clinical Global Impression – Improvement (CGI-I)					X	X	
Treatment with ClariFix			X				
Pain Numeric Rating Scale			X				
Adverse Event review and evaluation a			X			X	X
Study Exit						X	

a. AEs to be collected beginning at treatment timepoint. Any AEs experienced between Consent to Treatment timepoints should be evaluated for continued eligibility and suitability for study participation and may be documented as medical history, if applicable.
 
b. Unscheduled Visit activities to be completed based on reason for Visit and discretion of the Investigator.
 
c. Physical/Endoscopic Nasal Exam may be performed at the discretion of the Investigator in the event of a new or continuing AE.
							

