## 3 OBJECTIVES AND ENDPOINTS

The study overall objective is to evaluate the feasibility of treatment to the posterior nasal nerve at both the middle and inferior meatus locations within the nasal cavity for improvement in the symptoms of chronic rhinitis.

OBJECTIVES	ENDPOINTS
Primary	
Evaluate the safety of treatment to the inferior meatus location	Incidence of procedure related Serious Adverse Events (SAEs) and/or Serious Adverse Device Effects (SADE)
Secondary	
Evaluate the effectiveness and tolerability of treatment at the inferior meatus location	
 
1. Incidence of procedure-related Adverse Events (AEs) or Adverse Device Effects (ADEs).
 
2. Tolerability of treatment via verbal report of pain/discomfort.
 
3. Nasal symptoms using rTNSS scale at 30- and 90-Days post-treatment.
 

Tertiary/Exploratory	
Physician Evaluation of ease of treatment delivery using study device for inferior meatus location.	Physician-reported ease-of-use rating.

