### 8.3.2 PAIN NUMERIC RATING SCALE

A pain numeric rating scale (NRS) for pain function best for the patient's subjective feeling of the intensity of pain right now—present pain intensity. The NRS utilizes an 11-point scale of zero to 10. Subjects verbally report pain on the scale of 0 to 10 with zero representing “no pain” and 10 representing “worst pain imaginable”.

Pain and/or discomfort during the Treatment Visit (Visit 3) will be collected for each individual freeze treatment location (left middle meatus, left inferior meatus, right middle meatus, and Right Inferior Meatus), and any post-treatment pain and/or discomfort reported immediately following the treatment.

---

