4.4 Outcome variables

4.4.1 Efficacy outcome variables

The following outcome variables will be collected and analyzed as primary, secondary, or exploratory efficacy outcomes:

- Procedure pain scores (NPRS): during the procedure and immediately post procedure
- rTNSS: collected at baseline and at 30-day and 90-day follow-up visits
- Quantitative nasal endoscopy scores: collected at baseline, procedure, and at 30-day and 90-day follow-up visits
- NOSE: collected at baseline and at 30-day and 90-day follow-up visits
- SNOT-22: collected at baseline and at 30-day and 90-day follow-up visits
- Nasal symptom VAS: collected at baseline and at 30-day and 90-day follow-up visits
- Mini RQLQ: collected at baseline and at 30-day and 90-day follow-up visits

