7.2 Efficacy outcomes

7.2.1 Procedure pain/discomfort

A secondary endpoint is the tolerability of the procedure. Current intensity of pain/discomfort is verbally provided by the participant during the procedure for each treatment location and overall immediately post procedure. Pain/discomfort is assessed using the 11-point NPRS where 0 indicates no pain/discomfort and 10 indicates the worst pain/discomfort imaginable.¹

The count and percentage of participants indicating pain and the mean \pm SD pain score will be calculated. The termination of any procedure due to pain will also be noted.

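### Protocol 8.1.3 conditions the post-procedure pain score on having pain, while SAP 4.4.1 and 7.2.1 define that score without a condition (low severity)

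*Protocol*

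**What the plan says.** Protocol section 3 lists as a secondary endpoint "Tolerability of treatment via verbal report of pain/discomfort". Two steps of Protocol 8.1.3 collect the scores.

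- Step 2a covers the treatment locations and carries no condition: "Subject will be asked for a Verbal Pain Numeric Rating Scale (NRS) immediately after cryoablation treatment at each individual treatment location".
- Step 3a, under adverse event monitoring, does carry one: "Should post-procedure discomfort or pain be experienced, in addition to an adverse event form, subject will be asked for a Verbal Pain NRS".

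Protocol 8.3.2 covers the four location scores and adds "any post-treatment pain and/or discomfort reported immediately following the treatment". The same section makes 0 a valid answer: "Subjects verbally report pain on the scale of 0 to 10 with zero representing" the absence of pain. The Schedule of Activities (Protocol 1.3) marks the "Pain Numeric Rating Scale" at Visit 3 with no footnote.

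SAP 4.4.1 lists "Procedure pain scores (NPRS): during the procedure and immediately post procedure". SAP 7.2.1 describes the score as "verbally provided by the participant during the procedure for each treatment location and overall immediately post procedure". It plans the number and percentage of participants who indicate pain, and a mean with SD, but does not say which of the scores these cover. SAP 7.1 restricts section 7 outcomes to treated participants with one or more valid assessments at follow-up.

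Protocol 9.4.1 works from available data without imputation, takes percentages over non-missing values, and includes n in summaries of continuous data. SAP 10.4 plans no missing-data analysis.

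**The concern.** Under step 3a, whether a post-procedure score exists depends on the quantity being measured. A participant without pain has no score rather than a score of 0. The SAP treats the same score as a routine measurement, and nothing links the two.

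At stake is one descriptive component of the tolerability endpoint. A mean over participants in pain, presented as the mean for the treated group, would make the period after the procedure look worse than it was. The percentage indicating pain at that timepoint would lose its meaning if only participants with pain have a value.

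**Working it through.** The documents give no expected pain score or pain rate, so there is no stated figure to reproduce. The check compares the passages and then sizes the effect under stated assumptions.

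**Does any passage supply the missing scores?**

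1. Step 2a asks after each location. It gives four scores, not an overall one.
2. Step 3a is the only visit step that asks for a score after the procedure, and it is conditional.
3. Protocol 8.3.2 speaks of pain that is reported. This does not remove the condition.
4. The Visit 3 mark in the Schedule of Activities is already met by the four location scores, so it does not establish a fifth score for everyone.
5. No passage says to enter 0 for a participant who was not asked, and Protocol 9.4.1 rules out imputing it.

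**Inputs for the size**

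- N = 30 treated participants (SAP 3.1.3).
- k = number with post-procedure pain: not in the documents, varied from 6 to 30.
- m = mean score among those in pain: assumed 2, 4 or 6.
- Those not asked would have scored 0. This follows from step 3a, since anyone with discomfort would have been asked.

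**Formulas**

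- Mean reported under conditional collection = m.
- Mean if all are asked = (k × m + (30 − k) × 0) / 30 = k × m / 30.
- Factor = m / (k × m / 30) = 30 / k.
- Excess in points = m × (1 − k / 30).
- Percentage in pain over all treated = k / 30. Over non-missing scores it is about 100% for every k.

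| k | k/30 | Factor 30/k | Excess, m = 2 | m = 4 | m = 6 |
|---|---|---|---|---|---|
| 6 | 20% | 5.0 | 1.6 | 3.2 | 4.8 |
| 10 | 33% | 3.0 | 1.3 | 2.7 | 4.0 |
| 15 | 50% | 2.0 | 1.0 | 2.0 | 3.0 |
| 20 | 67% | 1.5 | 0.7 | 1.3 | 2.0 |
| 25 | 83% | 1.2 | 0.3 | 0.7 | 1.0 |
| 30 | 100% | 1.0 | 0 | 0 | 0 |

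Worked row: k = 10 and m = 4 give an all-treated mean of 10 × 4 / 30 = 1.33 against a reported 4, an excess of 2.67.

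The SD also changes, but in no fixed direction. With SD s among those in pain and M = k × m / 30, the all-treated SD is √{[(k − 1)s² + k(m − M)² + (30 − k)M²] / 29}. For assumed m = 3 and s = 1.5 it is 1.37, 1.76, 1.89 and 1.81 at k = 6, 12, 18 and 24, against 1.5 under conditional collection.

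**The case against.** Step 3a sits under adverse event monitoring and is tied to an adverse event form, so it may be meant only to characterise an event. It does not say that nobody else is asked. The case report form is not in the documents and may ask everyone. This stands as a limit on certainty: the mismatch in wording is established, the resulting bias is not. It does not close the gap, because on that reading no visit step collects the routine overall score that the SAP defines.

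The plan also has partial safeguards. Protocol 9.4.1 calls for n, so a reduced number would show. Step 3a pairs post-procedure pain with an adverse event form, and Protocol 9.4.4 reports event incidence as number and percentage of subjects, which SAP 8.1 bases on everyone treated. The number with post-procedure pain should therefore appear in part elsewhere. This stands and lowers the severity.

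A reader might infer three stronger things that the documents do not support.

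- That pain at the inferior meatus, the location named in the objective, is overstated. The location scores are collected without condition under step 2a.
- That the mean and SD of SAP 7.2.1 certainly summarise the overall score. The section does not say which scores they cover.
- That the SAP gives the pain scores no analysis population, so the safety population can simply be written into 7.2.1. SAP 7.1 sets the cohort for section 7, and changing 7.2.1 alone would contradict it.

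**Conclusion.** The point holds, at low severity. The Protocol and SAP disagree on who gives the overall post-procedure score. If step 3a is followed as written and the 7.2.1 mean and SD are applied to that score, they describe participants in pain only. The overstatement of the mean is N/k, from 5.0 at k = 6 to none at k = 30; k is an assumption throughout, so this is a range and not a prediction. The percentage indicating pain approaches 100% only if the non-missing denominator of Protocol 9.4.1 is used; over the full cohort it can be recovered.

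Neither document plans a hypothesis test that depends on this score, and the main tolerability evidence by location is untouched. If the case report form already asks everyone, only the wording needs correcting.

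**What to change.** - **Collection.** Reconcile Protocol 8.1.3 step 3a and 8.3.2 with SAP 7.2.1 so that every treated participant gives the immediate post-procedure score, with 0 allowed.
- **Summary.** State in SAP 7.2.1 that the per-location and overall scores are summarised separately.
- **Cohort.** Decide whether these Day 0 scores are reported over all treated participants. If so, amend SAP 7.1 and 7.2.1 together; if not, use the 7.1 cohort and say so.
- **If data were already collected conditionally.** Report the number with post-procedure pain over the stated cohort, and label the mean and SD as applying to participants reporting pain. Do not set unasked scores to 0.

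The cost is one more verbal question per participant at a visit that already takes four scores, and a few lines of text. If collection is finished, only a denominator and a table label change.

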#### 8.1.4 7-DAY FOLLOW-UP VISIT (VISIT 4) (DAY 7)

Subjects will return to the office at one (1) week ( $\pm 3$  days) from Visit 3 for the 1-Week Follow-up Visit (Visit 4).

At Visit 4, the following study activities will be completed:

1. Concomitant Medication usage will be updated.
2. Subject will be assessed for any new Adverse Events experienced since Visit 3 and/or review of previously unresolved Adverse Events.
3. If a continuing or new study-related AE, Physician may choose to complete a Physical Nasal Exam (see Section 8.3.1) and document findings.
4. Subject will be scheduled for 1-Month Follow-up visit (Visit 5).

---

#### 8.1.5 1-MONTH FOLLOW-UP VISIT (VISIT 5) (DAY 30)

Subjects will return to the office at thirty (30) days ( $\pm 7$  days) from Visit 3 for the 1-Month Follow-up Visit (Visit 5).

At Visit 5, the following study activities will be completed:

1. Subject will complete rTNSS, NOSE, SNOT-22, VAS for Nasal Symptoms and MiniRQLQ questionnaires.
2. Concomitant Medication usage will be updated.
3. Subject will be assessed for any new Adverse Events experienced since Visit 4 and/or review of previously unresolved Adverse Events.
4. Physician will complete Physical Nasal Exam and document findings.
5. Investigator will complete Clinical Global Impression—Improvement (CGI-I) scale (see Section 8.2.5).
6. Subject will be schedule for 3-Month Follow-up visit (Visit 6).

---

#### 8.1.6 3-MONTH FOLLOW-UP VISIT (VISIT 6) (DAY 90)

Subjects will return to the office at ninety (90) days ( $\pm 14$  days) from Visit 3 for the 3-Month Follow-up Visit (Visit 6).

At Visit 6, the following study activities will be completed:

1. Subject will complete rTNSS, NOSE, SNOT-22, VAS for Nasal Symptoms and MiniRQLQ questionnaires.
2. Concomitant Medication usage will be updated.
3. Subject will be assessed for any new Adverse Events experienced since Visit 5 and/or review of previously unresolved Adverse Events.
4. Physician will complete Physical Nasal Exam and document findings.
5. Investigator will complete Clinical Global Impression—Improvement scale (see Section 8.2.5).
6. Investigator will complete the Study Exit form.

Subject participation will be complete at the Visit 6 time point.

---

#### 8.1.7 UNSCHEDULED VISITS

An Unscheduled Visit (UV) may occur after Visit 3 through the end of the study participation. A UV may occur due to a study-related adverse event.

The following activities will be completed as part of a UV:

- Concomitant Medication usage will be updated.
- Subject will be assessed for any new Adverse Events experienced since previous Visit and/or review of previously unresolved Adverse Events.

Additional data may be collected and documented at the discretion of the Investigator. Activities that may be completed at the Investigator's discretion is as follows:

- Physical Nasal Exam

- Physician completed CGI-I

## 8.2 EFFICACY ASSESSMENTS

### 8.2.1 REFLECTIVE TOTAL NASAL SYMPTOM SCORE (rTNSS)

The primary effectiveness endpoint will be assessed based on the four-symptom reflective Total Nasal Symptom Score (rTNSS) (See Addendum: Patient Questionnaires). rTNSS is a validated symptom severity scoring system that consists of the sum of four (4) individual subject-assessed symptom scores for rhinorrhea, nasal congestion, nasal itching, and sneezing. Each item is scored on a scale of 0 (No Symptoms) to 3 (Severe Symptoms) and is based on the subject's evaluation of symptom severity over the preceding two (2) weeks at study visits. The four-symptom rTNSS has a possible score of 0-12. The reflective scores will be based on the subject's evaluation of symptom severity over the preceding two (2) week period.

In this study, a modified version of the rTNSS will be utilized that adds two additional questions for rating of post-nasal drip and clearing of throat. However, these will not be included in the analysis of the 4-item rTNSS and will be analyzed separately.

Subjects will be asked to assess their symptoms at the Screening Visit (Visit 1), Baseline Visit (Visit 2) (if on a day other than Screening), and at the 1-Month (Visit 5) and 3-Month Follow-up (Visit 6) Visits. The subjects will be asked to assess each symptom individually (runny nose, congestion, nasal itching, sneezing) (See Addendum: Patient Questionnaires). Subject may be reminded of baseline score prior to treatment, as appropriate.

### 8.2.2 NASAL OBSTRUCTION AND SEPTOPLASTY EFFECTIVENESS (NOSE) SURVEY

The Nasal Obstruction and Septoplasty Effectiveness (NOSE) survey consists of 5 items, each scored using a 5-point Likert scale to make a total score range of 0 to 100. The subject completes the survey by circling the response closest to describing their current symptoms over the past 1 month (See Addendum: Patient Questionnaires). The sum of those responses is multiplied by a factor of 5 to base the scale out of a possible score of 100 for analysis. Higher scores indicate worse obstruction.

The NOSE survey will be administered at the Baseline (Visit 2), and 1- (Visit 5) and 3-Month (Visit 6) Follow-up Visits.

### 8.2.3 SINO-NASAL OUTCOME TEST (SNOT-22)

The Sino-Nasal Outcome Test (SNOT-22) is a validated patient-reported questionnaire to assess the impact of nasal symptoms on a patient's quality of life. The questionnaire consists of 22 categories, each scored using a 5-point Likert scale (0 = No Problem to 5 = Problem as bad as it can be). The subject completes the survey by circling the response closest to describing "how bad" their current symptoms are in each category over the past two (2) weeks, and then checks up to five (5) categories that are the "Most Important Items" affecting their health (See Addendum: Patient Questionnaires). The sum of the responses produces a total possible score of 0 to 110 for analysis. Higher scores indicate worse obstruction.

The SNOT-22 questionnaire will be administered at the Baseline (Visit 2), and 1- (Visit 5) and 3-Month (Visit 6) Follow-up Visits.

---

#### 8.2.4 MINI RHINOCONJUNCTIVITIS QUALITY OF LIFE QUESTIONNAIRE (MINIRQLQ)

The Mini Rhinoconjunctivitis Quality of Life Questionnaire (MiniRQLQ) is a validated tool that measures the functional (physical, emotional, and social) problems associated with rhinitis (See Addendum: Patient Questionnaires). The MiniRQLQ was adapted from the original 28-item Rhinoconjunctivitis Quality of Life Questionnaire (RQLQ), which included 28-items in 7 domains (sleep, non-Rhinoconjunctivitis symptoms, practical problems, nasal symptoms, eye symptoms, activity limitations, and emotional function). The MiniRQLQ is a 14-item questionnaire that covers 5 domains of activities, practical problems, nose symptoms, eye symptoms, and other symptoms. Subjects are asked to recall impairments experienced during the previous week and to respond to each item on a 7-point scale (0 = no impairment, 6 = maximum impairment). The overall RQLQ score is the mean of all 14 responses and the individual domain scores are the means of the items in those domains.

The MiniRQLQ questionnaire will be administered at the Baseline (Visit 2), and 1- (Visit 5) and 3-Month (Visit 6) Follow-up Visits.

---

#### 8.2.5 VISUAL ANALOG SCALE – NASAL SYMPTOMS

A Visual Analog Scale (VAS) is a measurement instrument that tries to measure a characteristic or attitude that is believed to range across a continuum of values and cannot easily be measured. It is often used in epidemiologic and clinical research to measure the intensity or frequency of various symptoms. From the subject's perspective, this spectrum appears continuous and does not make discrete jumps, as a categorization of none, mild, moderate and severe would suggest.

In this study, a 100mm scale (see Addendum: Patient Questionnaires) will be used to evaluate the individual symptoms over the last week of rhinitis (runny nose), nasal congestion (stiffness), and overall nasal symptoms. Subjects will report record their symptoms, based on the last week, on a continuum of 0mm on the left, representing no symptoms, to 100mm on the right, representing severe symptoms.

The VAS for Nasal Symptoms will be administered at the Baseline (Visit 2), and 1- (Visit 5) and 3-Month (Visit 6) Follow-up Visits.

---

#### 8.2.6 CLINICAL GLOBAL IMPRESSION – IMPROVEMENT (CGI-I)

The Clinical Global Impression--Improvement (CGI-I) rating scales is a clinician completed subject assessment of the changes of symptoms since time of treatment based on their clinical experience. The CGI-I is a 7-point Likert scale that ranges from a scale of 1 being "Very Much Improved" to 7 being "Very Much Worse".

The CGI-I will be completed that the 1- (V5) and 3-Month (V6) Follow-up Visits at the completion of the Physical Nasal Exam (See Section 8.3.1). Additionally, the CGI-I may, at the discretion of the clinician, be administered at an Unscheduled Visit (See Section 8.1.7).

---

### 8.3 SAFETY AND OTHER ASSESSMENTS

---

#### 8.3.1 PHYSICAL NASAL EXAM

A physical nasal evaluation of the treatment area and nasal cavity will be performed by a licensed clinician via endoscope at the Screening (Visit 1), 1-Week (Visit 4 due to AE occurrence or monitoring), 1-Month (Visit 5) and 3-Month (Visit 6).

**IMPORTANT:** Except for 1-Week (Visit 4), if applicable, subjects are not to be decongested prior to the Physical Nasal Exam.

Prior to decongestant, bilateral endoscopic videos or images are to be collected capturing the head of the inferior and middle turbinates (see Section 8.3.3).

The clinician will assess each side of the nasal cavity for hypertrophy of the middle and inferior turbinates and congestion using a 0 to 3 scale (0=None, 1=Mild, 2=Moderate, or 3=Severe).

After decongestant, a second bilateral endoscopic videos or images are to be collected capturing the head of the inferior and middle turbinates.

At Visit 4 (if applicable), Visit 5 and Visit 6, the clinician will assess each treatment area (left middle meatus, left inferior meatus, right middle meatus and right inferior meatus) for bleeding, crusting, and swelling using the same scale of 0 to 3.

An endoscopic exam may be completed at an Unscheduled Visit at the discretion of the Investigator, in the event of a study-related adverse event.

---

### 8.3.2 PAIN NUMERIC RATING SCALE

A pain numeric rating scale (NRS) for pain function best for the patient's subjective feeling of the intensity of pain right now—present pain intensity. The NRS utilizes an 11-point scale of zero to 10. Subjects verbally report pain on the scale of 0 to 10 with zero representing “no pain” and 10 representing “worst pain imaginable”.

Pain and/or discomfort during the Treatment Visit (Visit 3) will be collected for each individual freeze treatment location (left middle meatus, left inferior meatus, right middle meatus, and Right Inferior Meatus), and any post-treatment pain and/or discomfort reported immediately following the treatment.

---

